6.2. Secondary Objectives and Endpoints

Part 1

The secondary objective of Part 1 of this study is:

- To examine the PK of Nusinersen in subjects with SMA who are not eligible to participate in the clinical studies ISIS 396443-CS3B or ISIS 396443-CS4

The endpoint that relates to this objective is:

- Nusinersen concentrations in plasma and CSF

Part 2

The secondary objective of Part 2 of this study is:

- To examine the PK of Nusinersen in subjects with SMA who participated in Part 1 and completed their End of Part 1 Evaluation assessments

The endpoint that relates to this objective is:

- Nusinersen concentrations in plasma and CSF

The secondary immunogenicity endpoint is as follows:

- Plasma antibodies to Nusinersen

CONFIDENTIAL

The information contained herein may not be used, disclosed, or published without the written consent of Biogen MA Inc.

6.3. Exploratory Objectives and Endpoints

Part 1

The exploratory objective of Part 1 of this study is:

- To explore the efficacy of Nusinersen in subjects with SMA who are not eligible to participate in the clinical studies ISIS 396443-CS3B or ISIS 396443-CS4.

The endpoints that relate to this objective are:

- Change from baseline in ventilator use
- Attainment of motor milestones assessed by Section 2 of the Hammersmith Infant Neurological Examination (HINE)
- Change from baseline in growth parameters (body length, head circumference, chest circumference, arm circumference, weight for age, weight for length, and head to chest circumference ratio) through final safety follow-up evaluation
- Clinical Global Impression of Change (physician and caregiver assessment) through final safety follow-up evaluation

The exploratory immunogenicity endpoint is as follows:

- Plasma antibodies to Nusinersen

Part 2

The exploratory objective of Part 2 of this study is:

- To explore the efficacy of Nusinersen in subjects with SMA who participated in Part 1 and completed their End of Part 1 Evaluation assessments.

The endpoints that relate to this objective are:

- Change from baseline in ventilator use
- Attainment of motor milestones assessed by World Health Organization (WHO) motor milestones and Section 2 of the HINE
- Change from baseline in growth parameters (body length, head circumference, chest circumference, arm circumference, weight for age, weight for length, and head to chest circumference ratio) through Part 2 Final Follow-up Evaluation
- Clinical Global Impression of Change (physician and caregiver assessment) through Part 2 Final Follow-up Evaluation and Assessment of Caregiver Experience with Neuromuscular Disease (ACEND)

CONFIDENTIAL

The information contained herein may not be used, disclosed, or published without the written consent of Biogen MA Inc.

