The information contained herein may not be used, disclosed, or published without the written consent of Biogen MA Inc.

Statistical Methods: Analysis Population

The intent-to-treat population is defined as all subjects who are randomized and receive at least 1 dose of study treatment or sham procedure in Part 1.

The safety population will include all subjects who are randomized and receive at least 1 dose of study treatment or sham procedure in Part 1.

The PK population will include all subjects who are randomized and have at least 1 evaluable postdose or postsham-procedure PK sample.

Part 1**Safety Analysis**

The analysis of safety will be performed on the safety population. The incidence of treatment-emergent AEs and SAEs will be tabulated. Changes from baseline in clinical laboratory parameters, vital signs, and ECG parameters will be summarized. Incidence of clinically relevant changes from baseline in vital signs and ECGs will be summarized. Laboratory parameters will also be summarized using shift tables, as appropriate.

PK Analysis

Summary statistics for plasma and CSF concentrations of Nusinersen will be provided.

Exploratory Analysis

For continuous endpoints, the mean change from baseline will be estimated with 95% confidence limits. For categorical outcomes, the proportion of subjects attaining a specified category will be estimated. Selected endpoints may be pooled across subsets as appropriate.

Part 2

No formal statistical analyses will be performed. Descriptive statistics will be presented for safety and efficacy data collected.

Interim Analysis: No formal interim analyses are planned. However, if the Sponsor decides to terminate Part 1 early, data prior to the unblinding of the first subject in Part 1 may be archived; no analyses are planned to be conducted based on the archived data. Full analysis of Part 1 data will be done following database lock at the end of Part 1.

Sample Size Determination: Since this study is exploratory, sample size determination will not be based on power consideration. The sample size considered for this study will allow exploration of safety, tolerability, and selected efficacy endpoints in the selected study population.

CONFIDENTIAL

The information contained herein may not be used, disclosed, or published without the written consent of Biogen MA Inc.

Study Stopping
Rules:

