7. STUDY DESIGN

7.1. Study Overview

This is a Phase 2 multicenter study conducted in 2 parts. The study was originally designed as a randomized, double-blind, sham-procedure controlled study to assess the safety and tolerability and explore the efficacy of intrathecally administered Nusinersen up to approximately 14 months (from the first dose until End of Part 1 Evaluation). Based on emergent data from the Nusinersen clinical development program, the Sponsor may decide to terminate Part 1 early, and all subjects may then be offered the opportunity to be unblinded and transition to Part 2 prior to completion of all Part 1 evaluations. Part 2 is an OLE phase that will assess long-term safety and tolerability and explore the efficacy of intrathecally administered Nusinersen for approximately 24 additional months. In Part 1 of the study, up to 21 subjects will be randomized in a ratio of 2:1 to receive Nusinersen by intrathecal LP injection (n = 14) or to a sham procedure-control (n = 7). Randomization will be stratified based on age at onset of clinical signs and symptoms consistent with SMA: >6 months versus ≤6 months. In Part 2 of the study, all subjects who participated in Part 1, who completed their End of Part 1 Evaluation assessments, and who elected to enroll in Part 2 will receive Nusinersen by intrathecal injection.

Subjects who withdraw early from Part 1 will be encouraged to complete the End of Part 1 Evaluation assessments at the time of withdrawal. Subjects who withdraw early from Part 2 will be encouraged to complete the Part 2 Early Termination Evaluation assessments at the time of withdrawal.

See Section 4.1 for a schematic of the study design.

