Summary statistics will be presented throughout. For continuous endpoints, summary statistics will generally include number of subjects with data, mean, standard deviation, median, minimum and maximum. The mean changes from baseline will be estimated with 95% confidence intervals. For categorical endpoints, summary statistics will generally include: number of subjects dosed, number of subjects with data, and the percentage of those with data in each category. Frequency distributions will be presented as appropriate.

The statistical software, SAS® version 9.4 or above, will be used for all summaries and statistical analyses.

For Part 2, a limited number of summaries will be produced. The approach will be to preserve the Part 1 study groupings as follows for Safety and Efficacy population:

- Previous control.
- Previous ISIS 396443.
- Total (previous control and previous ISIS 396443).

For the integrated analyses, the Safety displays will be grouped as follows:

- Previous control, Part 1, from their first sham procedure in Part 1.
- Previous control, Part 2, from their first ISIS 396443 dose in Part 2.
- Previous ISIS 396443, Part 1 and 2, from their first ISIS 396443 dose in Part 1.
- Total (Previous control Part 2 and previous ISIS 396443 Part 1 and 2)

For the integrated analyses, the Efficacy displays will be grouped as follows:

- Previous control, Part 1, from their first sham procedure in Part 1.
- Previous control, Part 2, from their first ISIS 396443 dose in Part 2.
- Previous control, Part 1 and 2, from their first sham procedure in Part 1.
- Previous ISIS 396443, Part 1 and 2, from their first ISIS 396443 dose in Part 1.

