#### 4.2.1 Change in Ventilator use

In the statistical analysis of Part 1, for each subject the mean number of hours of ventilator was calculated amongst the periods. These periods were created from the first dose of Nusinersen or sham procedure to the nominal visit. (example Day 1: > from Day 1 to Day 15 visit; Day 15: from Day 15 inclusive to Day 29 visit). In Part 2 for each subject the mean number of hours will be calculated for a monthly interval (30 days) starting from the first dose of Nusinersen or sham procedure. The intervals will be: month 1 from Day 1 inclusive to Day 30, Month 2 from Day 30 inclusive to Day 60, and so on.

The change from baseline over time will be presented and a plot of both total and change from baseline will be presented.

For each subject, the total number of hours of ventilation support required during the study will be calculated and prorated according to number of days on study. The percentage of time on ventilator support in total and by type either invasive prophylactic, invasive treatment, or non-invasive prophylactic and not invasive treatment will be presented.

The different respiratory aids/therapies used will be listed

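### Mean change in ventilator hours with 95% limits, in groups planned at no more than 7 and 14 children, collapses to 0 to 0 if no child's hours change, and can cover well below 95% if only a minority change, mostly upward.

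*Protocol*

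**What the plan says.** Protocol 6.3 gives "Change from baseline in ventilator use" as the first exploratory efficacy endpoint in both parts. The synopsis, repeated in Protocol 16.3.2, sets the rule: "For continuous endpoints, the mean change from baseline will be estimated with 95% confidence limits". SAP section 2 has the same rule: "The mean changes from baseline will be estimated with 95% confidence intervals".

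SAP 4.2.1 makes ventilator use a continuous variable. For Part 1, "for each subject the mean number of hours of ventilator was calculated amongst the periods"; for Part 2 the same mean is taken over 30-day intervals. The change from baseline is then presented over time and plotted. This section does not repeat the 95% limits, and it does not exempt ventilator hours from them.

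Protocol 7.1 plans up to 21 children, 14 on Nusinersen and 7 on sham. The integrated efficacy displays in SAP section 2 keep the former sham children as their own groups (Part 1, Part 2, and both parts together), so each of those groups is planned at no more than 7.

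Neither document names an interval method or says what to do when every change in a group is zero.

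**The concern.** Many changes may be exactly zero. Protocol 8.2 excludes children already ventilated for at least 16 hours a day continuously for more than 21 days, and those with a permanent tracheostomy. Protocol 8.1 admits later-onset children, and early-onset children with 3 SMN2 copies. SAP 4.2 makes the diary obligation continuous only once a first use has been recorded, so it foresees children with none.

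A mean of 7 or 14 values, most of them zero and the rest mostly positive, is badly served by a symmetric interval. In the extreme case the interval has no width. A reader could take 0 to 0 in 7 sham children as certainty that ventilation need does not rise, when 7 children cannot show that. In less extreme cases the interval would tend to sit too low and so understate worsening.

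**Working it through.** **Inputs from the documents.** Nominal level 95%; planned group sizes 7 and 14; variable is change in mean hours.

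**Assumptions.** A Student t-interval, mean ± t(0.975, n−1)·SD/√n, because no method is named. The share p of children whose hours change is not given, so p = 0.1, 0.2, 0.3 and 0.5 are tried. Those who change rise by Uniform(2, 16) h and the others change by 0, so the true mean change is 9p hours.

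**Step 1: the nominal level.** With normally distributed changes, simulated coverage is 0.950 at n=7 and 0.950 at n=14. The 95% is right for such data, so any shortfall comes from the shape of the data.

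**Step 2: no child changes.** SD = 0, so the limits are 0 to 0 whatever the distribution. The chance of this is (1−p)^n. The Clopper-Pearson upper limit for 0 of n is 1 − 0.025^(1/n): 1 − 0.025^(1/7) = 0.410 and 1 − 0.025^(1/14) = 0.232.

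**Step 3: coverage when some change, all upward** (200,000 simulated groups per cell).

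| p | n=7: zero width | n=7: coverage | n=14: zero width | n=14: coverage |
|---|---|---|---|---|
| 0.1 | 47.8% | 52% | 22.9% | 72% |
| 0.2 | 21.0% | 75% | 4.4% | 86% |
| 0.3 | 8.2% | 84% | 0.7% | 91% |
| 0.5 | 0.8% | 92% | <0.1% | 94% |

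At n=7 and p=0.2 the interval lies wholly below the true mean in 25.4% of runs and wholly above it in 0.1%.

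**Step 4: other shapes, coverage for p = 0.1, 0.2, 0.3, 0.5.**
- Exponential increases, mean 6 h: 0.45, 0.64, 0.74, 0.83 at n=7; 0.62, 0.76, 0.82, 0.88 at n=14.
- Uniform increases of 8 to 16 h: 0.52, 0.79, 0.91, 0.94 at n=7; 0.77, 0.90, 0.93, 0.95 at n=14.
- Three quarters up and one quarter down, 0 to 12 h: 0.50, 0.73, 0.85, 0.93 at n=7; 0.71, 0.87, 0.92, 0.95 at n=14.
- Symmetric around zero, within ±12 h: 0.978 to 1.000 at n=7 and 0.954 to 0.999 at n=14. There is no shortfall.

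**Step 5: one child of 7 changes by x hours.** Mean = x/7 = 0.143x; SD = x/√7; SE = x/7; t(0.975, 6) = 2.447. The limits are 0.143x ± 0.350x, that is −0.21x to +0.49x.

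**The case against.** The strongest reply is that the size of the problem is assumed. The documents give neither the share of children whose hours change nor the direction. Lesser ventilator use is allowed at entry, 2-copy early-onset children older than 7 months are enrolled, and Protocol 5.1 describes respiratory failure as the usual cause of death in Type I disease, so most children might change. What counts is zero change, not zero hours: a child on stable support contributes about zero, and one who is weaned contributes a negative value. This stands, and it makes the coverage figures conditional.

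A reader might infer that the limits fall short of 95% whatever the data. They do not: at 50% changing with bounded increases the shortfall is mild, and with symmetric changes there is none. A reader might also call a lower limit below zero impossible. For a change it means fewer hours, which is impossible only if every child in the group starts at zero. The documents do not say so.

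It can also be said that 41% concerns a share of children while the planned interval concerns a mean in hours. That is correct; the comparison shows only how little 7 children can exclude.

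Finally, the SAP already plans the SD, median, minimum and maximum, the percentage of time on support, and time to death or permanent ventilation. These help, and an all-zero group would be visible in them. But SAP 4.2.1 plans no count of children with any use or with an increase. The percentage of time is another average with many potential zeros, and the permanent-ventilation endpoint misses a child who starts a few hours a night.

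The Part 1 analysis is in a separate SAP that was not supplied, so its handling cannot be checked. The integrated displays in the supplied SAP still include the small sham groups. Protocol section 16 promises only descriptive statistics for Part 2, but the interval rule in SAP section 2 makes no exception for it.

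**Conclusion.** The point holds in conditional form. It follows from the documents that mean change in ventilator hours receives 95% limits in groups planned at no more than 7 and 14. With the usual interval for a mean, those limits are 0 to 0 if no child's hours change; this needs no distributional assumption.

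Poor coverage is a risk, not a certainty. It rests on a t-interval, on a minority of children changing, and on the changes being mostly upward. Under those conditions coverage at n=7 runs from about 52% (10% changing) to 84% (30% changing), and at n=14 from 72% to 91%, with nearly all misses on the low side.

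Severity is minor: the endpoint is exploratory, and no test or decision depends on it.

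**What to change.** In SAP 4.2.1, for each interval and display group:
- Report the number and percentage of children with any ventilator use, and with an increase from baseline, each with Clopper-Pearson 95% limits.
- Report the median, quartiles, minimum and maximum of the change in hours.
- Keep the mean change and its plot as description, and state that ventilator hours are exempt from the 95% limits in SAP section 2 and Protocol 16.3.2.

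The data are already collected. The cost is a sentence or two of SAP wording and one more table shell. The downside is that the exact intervals are wide: 0% to 41% for 0 of 7, and 0.4% to 58% for 1 of 7.

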7. STUDY DESIGN

7.1. Study Overview

This is a Phase 2 multicenter study conducted in 2 parts. The study was originally designed as a randomized, double-blind, sham-procedure controlled study to assess the safety and tolerability and explore the efficacy of intrathecally administered Nusinersen up to approximately 14 months (from the first dose until End of Part 1 Evaluation). Based on emergent data from the Nusinersen clinical development program, the Sponsor may decide to terminate Part 1 early, and all subjects may then be offered the opportunity to be unblinded and transition to Part 2 prior to completion of all Part 1 evaluations. Part 2 is an OLE phase that will assess long-term safety and tolerability and explore the efficacy of intrathecally administered Nusinersen for approximately 24 additional months. In Part 1 of the study, up to 21 subjects will be randomized in a ratio of 2:1 to receive Nusinersen by intrathecal LP injection (n = 14) or to a sham procedure-control (n = 7). Randomization will be stratified based on age at onset of clinical signs and symptoms consistent with SMA: >6 months versus ≤6 months. In Part 2 of the study, all subjects who participated in Part 1, who completed their End of Part 1 Evaluation assessments, and who elected to enroll in Part 2 will receive Nusinersen by intrathecal injection.

Subjects who withdraw early from Part 1 will be encouraged to complete the End of Part 1 Evaluation assessments at the time of withdrawal. Subjects who withdraw early from Part 2 will be encouraged to complete the Part 2 Early Termination Evaluation assessments at the time of withdrawal.

See Section 4.1 for a schematic of the study design.

7.2. Overall Study Duration and Follow-Up

Part 1 of the study will consist of a Screening Period, Treatment Period, and post-treatment End of Part 1 Evaluation. For subjects who meet eligibility criteria and enroll in Part 1, the duration of Part 1 will be approximately 15 months (450 days) and will include a Screening Period of no greater than 28 days, a 302-day Treatment Period, and an End of Part 1 Evaluation approximately 4 months after the last dose. Based on emergent data from the Nusinersen clinical development program, the Sponsor may decide to terminate Part 1 early, and all subjects may be offered the opportunity to transition to Part 2 prior to completion of all Part 1 evaluations.

Part 2 will consist of a Treatment Period and a post-treatment Final Follow-up Evaluation. For subjects who meet eligibility criteria and enroll in Part 2, the duration of Part 2 will be approximately 28 months and will include an open-label Treatment Period of approximately 24 months and a Part 2 Final Follow-up Evaluation approximately 4 months after the last dose of study treatment in Part 2.

Total study duration for subjects who participate in both Part 1 and Part 2 will be approximately 43 months.

CONFIDENTIAL

The information contained herein may not be used, disclosed, or published without the written consent of Biogen MA Inc.

7.2.1. Screening

Subject eligibility for Part 1 of the study will be determined within 4 weeks (Day -28 to Day -1) prior to the first injection of Nusinersen or administration of sham procedure and will be confirmed before randomization. If a subject initially fails any of the screening criteria, they will be allowed to be rescreened 1 time during the Screening Period at the discretion of the Investigator. End of Part 1 Evaluation assessments will be used to confirm subjects' eligibility for Part 2.

7.2.2. Treatment

Part 1

Eligible subjects will be admitted to the study site on Part 1 Day 1, undergo predose evaluations, and then receive an LP injection of Nusinersen or a sham procedure. After the injection on Day 1, subjects will remain at the study site for at least 24 hours after the procedure for safety monitoring.

Subjects will return to the study site on Days 15, 29, 64, 183, and 302 (± 1 day for Days 15 and 29 and ± 7 days for all other days) for follow-up evaluations and subsequent injections of study treatment or sham procedure, for a total of 6 injections or sham procedures over a dosing period of 10 months. During these 5 evaluations, all subjects will remain at the study site for at least 6 hours postdose for safety monitoring. An overnight stay is optional, at the discretion of the Investigator. Safety monitoring by telephone contact will occur on the day after injection of study treatment or sham procedure. In addition, the study site will monitor the subject's condition through telephone contact every other week (excluding weeks with study visit) throughout the study period.

After completing the End of Part 1 Evaluation assessments, all eligible subjects may elect to enroll in Part 2.

Based on emergent data from the Nusinersen clinical development program, the Sponsor may decide to terminate Part 1 early, and all subjects may be offered the opportunity to transition to Part 2 prior to completion of all Part 1 Evaluation assessments. All subjects enrolled in the study at the time of Sponsor termination will be considered Part 1 completers. The next study evaluation for those subjects will serve as an End of Part 1 Evaluation, which may occur at any time prior to the next scheduled Part 1 study evaluation.

Unblinding will occur in order for the subjects to transition from Part 1 to Part 2.

End of Part 1 Evaluation assessments are required to be done prior to the transition to Part 2. After performing the End of Part 1 Evaluation assessments, the subject may immediately transition to Part 2.

Part 2

Part 2 study procedures and schedules will be determined based on the subject's treatment assignment in Part 1.

CONFIDENTIAL

The information contained herein may not be used, disclosed, or published without the written consent of Biogen MA Inc.

Subjects who were randomized to receive Nusinersen in Part 1

End of Part 1 Evaluation assessments will be used to determine subject eligibility for Part 2 of the study. For subjects who were receiving Nusinersen in Part 1, Part 2 Day 1 will occur following the End of Part 1 Evaluation or approximately 4 months following the last injection of Nusinersen in Part 1. On Part 2 Day 1, these subjects will undergo predose evaluations according to the schedule of events ([Table 3](#)) and then receive their first dose of Nusinersen for Part 2 (next maintenance dose).

Subjects will return to the study site on Days 120, 239, 358, 477, 596, and 715 (± 7 days for all days) for follow-up evaluations and subsequent injections of Nusinersen over a dosing period of approximately 24 months. Subjects will remain at the study site for at least 1 hour postdose for safety monitoring and can be discharged at the discretion of the site Investigator and in compliance with the institutional requirements once the subjects have adequately recovered from the dosing procedure. An overnight stay is optional, at the discretion of the Investigator. Safety monitoring by telephone contact will occur on the day after injection of study treatment. In addition, the study site will monitor the subject's condition through telephone contact every other week (excluding weeks with study visit) throughout the study period.

Subjects who were randomized to receive sham procedure in Part 1

End of Part 1 Evaluation assessments will be used to determine subject eligibility for Part 2 of the study. For subjects who were receiving sham procedure in Part 1, Part 2 Day 1 will occur following the End of Part 1 Evaluation or as soon as possible following their End of Part 1 Evaluation, in the event of early termination by the Sponsor due to emergent data from the Nusinersen clinical development program. On Part 2 Day 1, these subjects will undergo predose evaluations according to the schedule of events ([Table 4](#)) and then receive their first injection of Nusinersen (first loading dose). Subjects will remain at the study site for at least 24 hours after the procedure for safety monitoring.

Subjects will return to the study site on Days 15, 29, 64, 183, 302, 421, 540, 659, and 778 (± 1 day for Days 15 and 29 and ± 7 days for all other days) for follow-up evaluations and subsequent injections of Nusinersen over a dosing period of approximately 24 months. Subjects will remain at the study site for at least 1 hour postdose for safety monitoring and can be discharged at the discretion of the site Investigator and in compliance with the institutional requirements once the subjects have adequately recovered from the dosing procedure. An overnight stay is optional, at the discretion of the Investigator. Safety monitoring by telephone contact will occur on the day after injection of study treatment. In addition, the study site will monitor the subject's condition through telephone contact every other week (excluding weeks with study visit) throughout the study period.

For both groups of subjects, Part 2 of the study will continue for approximately 24 months and in accordance with applicable laws and regulations. From Year 2 onwards, subjects will maintain evaluations for injection of study treatment every 4 months as indicated in [Table 3](#) and [Table 4](#).

CONFIDENTIAL

The information contained herein may not be used, disclosed, or published without the written consent of Biogen MA Inc.

